**Table 6-3 Time windows for analyses of tumor volume, patient reported outcome variables and gallbladder ultrasound**

Window name (1)	Window No.	Target Day	Starting Day of Window	Ending Day of Window
Baseline	1	-	-	1 (2)
Month 6	4	183	137	320
Month 12	6	365	321	458
Month 18	7	550	459	641
Month 24	8	731	642	821
Month 30	9	914	822	1005
Month 36	10	1096	1006	1187
After Month 36	11	-	1188	No upper limit
Last value on treatment		DLD (3)	2	DLD + gap (4)
Day 90 after last dose		DLD + 90 days	DLD+gap+1 days	DLD + 90 days

(1) Windows are named according to their target days. For example, the target day for window Month 6 is  $6 * 30.4375$  days, where 30.4375 is the standard length of a month ( $=365.25/12$ ). The starting day of the window is the midpoint between target day of previous window and current window and the ending day is the midpoint between target day of current window and next window.  
 Note that only post-baseline on-treatment assessments are assigned to windows Month 6, Month 12, etc., up to 'after Month 36'.  
 (2) For some parameters, the earliest assessment after first dose is used as baseline assessment if no assessment is available before or on the day of first dose. This assessment is then exclusively used as baseline assessment although it falls into a post-baseline window.  
 (3) DLD = Day of last dose of pasireotide s.c.  
 (4) gap = number of days after DLD during which assessments and events are considered on-treatment. gap=3 for efficacy analyses, gap=28 for safety analyses

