3.5 Visit schedule and assessments

This study is observational in nature and does not impose a therapy protocol, diagnostic/therapeutic interventions or a visit schedule. However, in order to help encourage more uniform data collection across study sites and patients a suggested schedule of assessments has been provided in [Table 3-1](#).

Patients will be treated with pasireotide s.c. according to the investigator's judgment and in accordance with the local (country-specific) pasireotide s.c. prescribing information. Available data will be collected at patients' visits to their site.

Table 3-1 Suggested schedule of assessments

Visit/Frequency	Baseline	Monthly	Every 3 months	Every 6 months	Every 12 months	End of Treatment	End Of study
Informed Consent	x						
Demography	x						
Inclusion/Exclusion Criteria	x						
Relevant medical history/Current medical conditions (history of smoking, history of alcohol use, presence of hepatitis B and C infections)	x						
Cushing's disease history	x						
Prior medications - For Cushing's Disease	x						
Coagulation test (Prothrombin time, APTT)	x					x	x
Vital Signs	x	x	x	x	x	x	x
Pregnancy test	x	x	x	x	x	x	x
Clinical symptoms of Cushing's disease	x		x			x	x
Glycemic status, FPG	x ¹	x ²				x ³	x ³
Glycemic status, HbA1c	x ¹		x			x ⁴	x ⁴
Salivary cortisol	x	x ⁵	x			x	x
Serum cortisol after dexamethasone	x	x ⁵	x			x	x
24 hour urine collection - Urinary free cortisol	x	x ⁵	x			x	x
Pituitary imaging local analysis (MRI/CT scan)	x				x	x	x
LFTs (ALT, AST, Alkaline phosphatase)	x ¹	x ⁶	x			x	x
12 lead ECG evaluation - local analysis	x ^{1,7}		x			x	x
Hematology/Blood Chemistry *	x			x		x	x
Thyroid function tests (TSH, Free T4)	x				x	x	x
Gallbladder imaging	x ¹			x	x	x	x
Cushing's syndrome QoL/ Euro QoL-5D health QoL/ Patient Reported outcome (PRO)	x			x		x	x

Visit/Frequency	Baseline	Monthly	Every 3 months	Every 6 months	Every 12 months	End of Treatment	End Of study
Dose Administration Record-Pasireotide s.c	x	At each visit				x	x
Adverse Events	x	At each visit				x	x
Concomitant Medication	x	At each visit				x	x

¹ prior starting treatment with pasireotide s.c
² self-monitoring of blood glucose and/or FPG every week for the 1st two to three months and periodically thereafter, as clinically appropriate.
³ Monitoring of FPG 4 weeks after the end of treatment
⁴ Monitoring of HbA1c 3 months after the end of treatment
⁵ every month for the first 3 month and then every 3 months

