The data will be summarized with respect to demographic and baseline characteristics, safety observations and measurements as well as efficacy assessments. Data will be summarized and displayed by time intervals based visit windows rather than by a strict visit schedule, in order to reflect the nature of this study. Details on definition of time windows will be provided in the Report and Analysis Plan (RAP). Furthermore, for patients who discontinue treatment prior to the 3-year observation period, their safety and efficacy parameters will be reported according to the time window that corresponds to 90 days from the Day of last dose of pasireotide s.c. Continuous variables will be summarized by number of patients, mean, standard deviation, minimum, median and maximum. Categorical variables will be summarized by absolute and relative frequencies. Counts of missing values for both continuous and categorical variables will be reported. Results with and without imputation will be reported.

Baseline assessment refers to the last assessment prior to the patient's first pasireotide s.c. dose recorded after the signing of the informed consent or acknowledging an equivalent document (e.g., written information) as per country regulation. For some assessment this definition maybe expanded to include the first assessment post the first pasireotide s.c. dose recorded after informed consent or an equivalent document (e.g., written information) as per country regulation.

In this study, the first analysis will occur at about 12 months after the first patient enters the study. After this first analysis there will be one analysis on a yearly basis. The final analysis will occur when all patients complete the study. The same analysis will be performed for all analyses time points.

Assessment time points are considered relative to first pasireotide s.c. dose recorded on or after the singing of the informed consent or acknowledging of an equivalent document (e.g., written information) as per country regulation, unless noted otherwise.

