### 6.1.7 Time windows

There is no visit schedule and no planned assessment in this non-interventional study. Assessment related data are collected as they become available during the study period. Therefore assessments are assigned to time windows based on the study day on which the assessment is performed. For mean UFC, the sample day of the first urine sample included in the calculation of mean UFC will be used for assignment to time windows.

If there are multiple values within a time window, the assessment closest to the target day of the time window will be used, if not indicated otherwise. If two assessments are equally close (e.g. 7 days before and 7 days after target day), the later will be used.

Time windows will be assigned according to the window schema in Table 6-2 if assessments are expected more frequently than every 6 months. Otherwise the time windows in Table 6-3 will be applied (e.g., for tumor volume, variables related to patient reported outcome questionnaires, findings of gallbladder ultrasound).

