**Table 6-2 Time windows**

Window name (1)	Window No.	Target Day	Starting Day of Window	Ending Day of Window
Baseline	1	-	-	1 (2)
Month 1	2	30	2	60
Month 3	3	91	61	136
Month 6	4	183	137	229
Month 9	5	275	230	320
Month 12	6	365	321	458
Month 18	7	550	459	641
Month 24	8	731	642	821
Month 30	9	914	822	1005
Month 36	10	1096	1006	1187
After Month 36	11	-	1188	No upper limit
Last value on treatment		DLD (3)	2	DLD + gap (4)
Day 90 after last dose		DLD + 90 days	DLD+gap+1 days	DLD + 90 days

(1) Windows are named according to their target days. For example, the target day for window Month 6 is  $6 * 30.4375$  days, where 30.4375 is the standard length of a month ( $=365.25/12$ ). The starting day of the window is the midpoint between target day of previous window and current window and the ending day is the midpoint between target day of current window and next window.  
 Note that only post-baseline on-treatment assessments are assigned to windows Month 1, Month 2, etc., up to 'after Month 36'.

(2) For some parameters, the earliest assessment after first dose is used as baseline assessment if no assessment is available before or on the day of first dose. This assessment is then exclusively used as baseline assessment although it falls into a post-baseline window.

(3) DLD = Day of last dose of pasireotide s.c.

(4) gap = number of days after DLD during which assessments and events are considered on-treatment. gap=3 for efficacy analyses, gap=28 for safety analyses

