### 6.2.3 Mixed model for repeated measures

The following SAS code will be used to fit the mixed model for repeated measures.

```
proc mixed;
  class patient window ;
  model outcome = window base /ddfm=kr;
  repeated window /patient = patient type=un;
  lsmeans window / cl;
run;
```

Here, `patient` denotes the patient identifier (e.g. SID1A), `window` the time window assigned, `outcome` the outcome variable (e.g. mean UFC), and `base` the corresponding baseline value.

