#### 8.2.1 Secondary efficacy endpoints

The secondary efficacy endpoints are as follows:

---

1. Proportion of patients with a mean UFC  $\leq$  ULN at 1, 3, 6, 12, 24 and 36 months after enrollment into the study.
2. The absolute and percentage change from baseline in biochemical measures of disease activity (mean UFC, serum cortisol, serum cortisol after dexamethasone, salivary cortisol, ACTH, fasting serum lipid profile (total cholesterol, HDL, LDL)) over time.
3. Proportion of patients achieving normalization of biochemical measures of disease activity (serum cortisol, serum cortisol after dexamethasone, salivary cortisol, ACTH) over time, where normalization refers to being within the upper and lower limit of normal ranges.
4. The absolute and percentage change from baseline in clinical signs and symptoms (blood pressure, body weight, body mass index, waist circumference) over time.
5. The proportion of patients with favorable shift from baseline in clinical symptoms of Cushing's disease over time.
6. The change from the last dose of pasireotide s.c. to 90 days after permanent discontinuation of pasireotide s.c. for patients who discontinue pasireotide s.c. prior to completing 3-year observation period. This change will be evaluated for all available continuous efficacy parameters.
7. The absolute and percentage change from baseline in tumor size over time.
8. The absolute and percentage change from baseline in patient reported outcome questionnaires (Cushing QoL and EURO QoL) over time.

All efficacy analyses will be done for all patients in the FAS and for the two cohorts. And all efficacy analyses except those under 5 will be done for the subgroup patients from German sites. Additionally, the efficacy analyses described under 1, 2, and 3 above will be repeated for the following subgroups of patients:

- Patients treated with monotherapy pasireotide s.c. throughout the study
- Patients treated with a combination of pasireotide s.c. with any other therapy for Cushing's disease throughout the study
- Patients who switched from monotherapy to combination therapy or vice versa at any time during the study

For all continuous efficacy variables (biochemical measures of disease activity, blood pressure, body weight, body mass index, waist circumference, tumor size), a Mixed Effects Repeated Measures Model will also be employed to assess the longitudinal changes in these variables.

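### SAP Table 6-3 ends the Month 6 window at Day 320, but its own midpoint rule gives Day 274, so among the monthly windows Day 275-320 values count for Month 6 although they are nearer Month 12

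*SAP*

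**What the plan says.** SAP Section 6.1.7 assigns each assessment to a window by study day. Table 6-2 serves assessments expected more often than every 6 months. Table 6-3, titled "Time windows for analyses of tumor volume, patient reported outcome variables and gallbladder ultrasound", serves the rest. Footnote (1), the same in both tables on this point, fixes the upper limit of each window as follows: "the ending day is the midpoint between target day of current window and next window". It sets the lower limit in the same way, halfway from the preceding target.

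The relevant rows are:

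- Table 6-3, Month 6: target 183, Days 137 to 320.
- Table 6-3, Month 12: target 365, Days 321 to 458.
- Table 6-2, Month 6: target 183, Days 137 to 229.
- Table 6-2, Month 9: target 275, Days 230 to 320.

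Table 6-3 has no Month 9 row, and its numbering skips Window No. 5. Where a patient has several values, Section 6.1.7 says: "If there are multiple values within a time window, the assessment closest to the target day of the time window will be used".

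SAP Sections 8.2.1.6, 8.2.1.7 and 8.4.5 report tumor volume, both quality-of-life instruments and gallbladder findings separately at Months 6, 12, 18, 24, 30 and 36. Section 8.2.1 also puts tumor size in the mixed model, and the code in Section 6.2.3, "model outcome = window base /ddfm=kr", uses the assigned window as the time factor. Protocol Section 6 leaves window definitions to the analysis plan.

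**The concern.** The printed rows and the rule beneath them cannot both be right. A programmer who follows the rows and one who follows the footnote will produce different Month 6 and Month 12 tables.

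Nothing else in the plan repairs this. Closest-to-target selection operates only within a window, so it cannot move a value from Month 6 to Month 12. A Day 275-320 value therefore counts for Month 6, or drops out of the monthly summaries if the patient has another value nearer Day 183. It may still serve as the last value on treatment. The Table 6-1 allowance for a post-dose baseline is 6 months for imaging and questionnaires, so it does not reach these days.

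Tumor size is where this matters most. Protocol Table 3-1 suggests pituitary imaging at baseline, every 12 months, and at the end of treatment and of study. A first annual scan done 45 to 90 days early may be the only scan in the first year. It would be shown as a Month 6 change, leaving Month 12 empty unless another scan falls on Days 321-458. The same label enters the tumor mixed model. The worst-value sensitivity analysis in SAP Section 8.2.1 would then fill the empty Month 12 cell although an observed scan nearer Month 12 than Month 6 exists.

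**Working it through.** **Source of the printed figure.** Day 320 can be reproduced from Table 6-2, which has a Month 9 target of 275: (275 + 365)/2 = 320. The Table 6-3 Month 6 row (137-320) is exactly the Table 6-2 Month 6 (137-229) and Month 9 (230-320) rows joined.

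**Footnote rule applied to Table 6-3.** End day = (current target + next target)/2.

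| Boundary | Midpoint | Printed end | Difference (days) |
|---|---|---|---|
| Month 6/12 | (183 + 365)/2 = 274 | 320 | +46 |
| Month 12/18 | (365 + 550)/2 = 457.5 | 458 | +0.5 |
| Month 18/24 | (550 + 731)/2 = 640.5 | 641 | +0.5 |
| Month 24/30 | (731 + 914)/2 = 822.5 | 821 | -1.5 |
| Month 30/36 | (914 + 1096)/2 = 1005 | 1005 | 0 |

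Unrounded targets do not help: (6 + 12) × 30.4375/2 = 273.9. Rounding accounts for at most 1.5 days at the other boundaries and cannot account for 46.

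**Reach of each window (days before/after target).**

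- As printed: Month 6 46/137, Month 12 44/93, Month 18 91/91, Month 24 89/90, Month 30 92/91, Month 36 90/91.
- With 274/275: Month 6 46/91, Month 12 90/93.

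**Days affected.** The Month 6 window has 320 - 137 + 1 = 184 days. Days 275 to 320 are 46 days, and 46/184 = 25%. Day 275 is 92 days from Month 6 and 90 from Month 12. Day 320 is 137 days from Month 6 and 45 from Month 12. Day 274 is an exact tie, 91 days from each.

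**Illustration for annual scans.** The documents do not give scan timing. Assume first annual scans are spread uniformly over whole days around Day 365:

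| Spread | Month 6, as printed | Month 6, with 274 | Month 12, as printed | Month 12, with 275 |
|---|---|---|---|---|
| ±45 days | 1/91 = 1% | 0% | 90/91 = 99% | 100% |
| ±60 days | 16/121 = 13% | 0% | 105/121 = 87% | 100% |
| ±90 days | 46/181 = 25% | 0% | 135/181 = 75% | 100% |
| ±120 days | 76/241 = 32% | 30/241 = 12% | 138/241 = 57% | 184/241 = 76% |

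At ±120 days, 27/241 = 11% fall in Month 18 either way.

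**Start of the Month 6 window.** Day 137 is also a Table 6-2 figure, the Month 3/Month 6 midpoint (91 + 183)/2. Table 6-3 has no Month 3 window, so Days 2-136 (135 days) belong to no monthly window. The Baseline row has no target day, so the footnote gives no midpoint to compare with. This is a question, not a contradiction.

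**The case against.** The best defence is that the rows are intended and only the footnote is stale. Month 6 equals Months 6 and 9 of Table 6-2 joined, Window No. 5 is skipped without renumbering, and Months 12 to 36 have the same limits in both tables. On that reading Month 12 has one definition for every parameter. The documents do not exclude this, but no text says it, and footnote (1) would then be false. One of the two has to change.

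A change of boundary could also disturb continuity. Gallbladder findings are among the yearly interim tables (SAP Section 2.2.1), and SAP Section 4.1 says the analyses are the same at every time point. If the interim tables used these windows, moving the boundary for the final report would make them less comparable, whereas correcting the footnote would not. Earlier SAP versions are not available to settle this.

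The harm in the worst-value analysis also needs care. If a patient has only one first-year scan, moving it to Month 12 leaves Month 6 empty instead, so the number of imputed cells does not fall. What improves is that the observed value sits at the nearer time point.

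Finally, the shares above rest on an assumed distribution centered on Day 365. At ±45 days the effect is negligible, and at ±120 days the part due to the boundary is 46/241 = 19%, not the full 32%. These points limit the size of the problem. They do not remove the contradiction.

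**Conclusion.** The point holds. Table 6-3 contradicts its own footnote by 46 days at the Month 6/Month 12 boundary, and no exception is stated anywhere. Among the monthly windows, values from Days 275-320 are placed in Month 6 although Month 12 is nearer. That the days are misplaced follows from the printed figures alone. How many patients are affected depends on visit timing, which the documents do not give: for first annual scans the uniform assumption puts 1% to 32% in Month 6 as printed, against 0% to 12% under the rule.

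The consequence is limited to secondary, exploratory results: by-window summaries of tumor volume, quality of life and gallbladder findings, and the tumor mixed model with its sensitivity analyses. Questionnaires and gallbladder imaging are suggested more often than tumor imaging, so the effect there is likely smaller. The primary adverse-event endpoint, the gallbladder shift tables and the changes after discontinuation do not depend on this boundary. It should be corrected before the final analysis, but it does not threaten the study's main conclusion.

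**What to change.** In Table 6-3, end Month 6 at Day 274 and start Month 12 at Day 275. This restores the plan's stated rule and brings the reach of Month 12 into line with the later windows. If a joined Month 6/Month 9 window was intended, keep the rows, say so in Section 6.1.7 with the reason, and correct footnote (1). In the same edit, state whether the Day 137 start of Month 6 is intended and that earlier post-baseline values enter no monthly summary.

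The cost is two table cells or one footnote, plus reprogramming of the window flags if the boundary moves. No extra data are needed. Some Month 6 counts would fall and Month 12 counts rise. Month 12 would cover Days 275-458 in Table 6-3 but Days 321-458 in Table 6-2, which needs a table note. If interim tables were produced with the printed rows, the final report should also note the change.

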Except for the analysis of change from end of treatment to 90 days later, the efficacy analyses will only consider on-treatment values, defined as values assessed before end of treatment + 3 days.

All assessments will be assigned to time windows based on the study day on which the assessment was performed. If there are multiple values within a time window, the assessment closest to the target day of the time window will be used, if not indicated otherwise. Further details including the start and end days of the time windows are available in Appendix 16.1.9 of the CSR.

The continuous efficacy parameters will be also evaluated through a couple of sensitivity analyses: the first will be imputing the worst value at that time window in case of missing data and the second on the patients with the full set of values. The same Mixed Model will be employed for both the analyses.

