#### *8.2.1.6 Absolute and percentage change from baseline in tumor size*

For time windows Month 6, 12, 18, 24, 30, and 36, absolute and percentage change from baseline in tumor volume will be summarized with descriptive statistics. Distribution-free 95% CIs will be given for the median changes. This summary will only include post-baseline evaluations for which the same method of evaluation (CT scan or MRI) as at baseline.

In addition, the absolute and percentage change from the last assessment while on pasireotide

s.c. to the last value during the 90 days after drug discontinuation will be summarized in a similar manner.

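### The 3-day efficacy gap also governs pituitary imaging, so an end-of-treatment scan taken later than that leaves the on-treatment tumor results and, without an earlier on-treatment scan, enters no specified change analysis

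*SAP*

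**What the plan says.** SAP Table 6-3 holds the windows for tumor volume, patient-reported outcomes and gallbladder ultrasound. Its footnote 4 defines the gap: "gap = number of days after DLD during which assessments and events are considered on-treatment". DLD is the day of last dose. The values are "gap=3 for efficacy analyses, gap=28 for safety analyses". Footnote 1 admits only on-treatment post-baseline assessments to the Month windows.

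SAP 8.2.1 repeats the rule for efficacy: "Except for the analysis of change from end of treatment to 90 days later, the efficacy analyses will only consider on-treatment values", which it goes on to describe as "defined as values assessed before end of treatment + 3 days".

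The Last value on treatment window runs from Day 2 to DLD+gap. The Day 90 after last dose window runs from DLD+gap+1 to DLD+90. For tumor size, SAP 8.2.1.6 plans the change from baseline at Months 6 to 36, and also the change from the last on-drug assessment "to the last value during the 90 days after drug discontinuation will be summarized in a similar manner".

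Protocol Table 3-1, in the row "Pituitary imaging local analysis (MRI/CT scan", suggests imaging at baseline, every 12 months, at End of Treatment and at End of Study. SAP 6.1.7 states that there is no visit schedule.

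**The concern.** A short gap is understandable for hormone levels under a twice-daily injection. It fits poorly with an annual pituitary scan. The SAP itself treats imaging as slow at the other end of treatment: Table 6-1 accepts a pituitary scan up to 6 months after the first dose as baseline in Cohort 2, but a UFC, cortisol or ACTH value only up to 1 week after.

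With annual imaging, a patient who stops in the first year may have the End of Treatment scan as the only post-baseline scan. If it falls a few days late, the patient drops out of the tumor-size change tables. Early stoppers include those withdrawn for unsatisfactory therapeutic effect (Protocol 3.4.1.1), so the loss may be selective.

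Tumor expansion is an important potential risk in Protocol 3.5.2.3. Pituitary imaging is not among the safety assessments in SAP 8.4, and the AESI list in Attachment 9.2 has no tumor-expansion category. SAP 8.2.1.6 and the mixed model are therefore the planned quantitative analyses of tumor size.

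**Working it through.** **Inputs.** From SAP Table 6-3: gap=3 or 28; Month 6 = Days 137–320, Month 12 = Days 321–458, Month 24 = Days 642–821. The imaging schedule is from Protocol Table 3-1. The lag from last dose to the End of Treatment scan is not stated and has to be assumed.

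**Step 1: where a scan at DLD+10 goes.** First-year stoppers are taken to have no earlier scan from Day 2 on. Later stoppers are taken to have one annual scan at Day 365.

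| DLD | Scan | gap=3 | gap=28 |
|---|---|---|---|
| 60 | Day 70 | Day 90 window (64–150); on-treatment window (2–63) empty; no pair | Last value on treatment (2–88); no Month window, as 70 < 137 |
| 150 | Day 160 | Day 90 window (154–240); no pair | Last value on treatment; Month 6 |
| 300 | Day 310 | Day 90 window (304–390); no pair | Last value on treatment; Month 6 |
| 400 | Day 410 | Day 90 window (404–490); paired with Day 365 | Last value on treatment; in Month 12 the Day 365 scan is nearer the target and is kept |
| 700 | Day 710 | Day 90 window (704–790); paired with Day 365 | Last value on treatment; Month 24 |

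Under gap=3 the first three patients have a post-baseline scan but no specified change. SAP 4.1 would report the value in the day-90 window, but SAP 8.2.1.6 specifies no change from baseline to that window.

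**Step 2: what the paired change measures.** Interval = scan day − earlier scan day. On-drug part = DLD − earlier scan day.

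- DLD 700: interval 710 − 365 = 345 days; on drug 700 − 365 = 335 days; 335/345 = 97%.
- DLD 400: interval 410 − 365 = 45 days; on drug 400 − 365 = 35 days; 35/45 = 78%.

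In both cases the summary is labelled as change after stopping, but only 10 days are off drug.

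**Step 3: share of scans beyond the gap.** For a lag uniform on days 0 to L (L ≥ 3), the share later than 3 days is (L − 3)/(L + 1).

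- L = 3: 0/4 = 0%
- L = 7: 4/8 = 50%
- L = 14: 11/15 = 73%
- L = 28: 25/29 = 86%
- L = 90: 87/91 = 96%

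For an exponential lag with mean m days it is exp(−3/m): 22% for m = 2 and 65% for m = 7. If half are scanned on the stop day and the rest uniformly over 0–28 days, it is 0.5 × 25/29 = 43%.

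With gap=28 the uniform share is (L − 28)/(L + 1) for L ≥ 28: 0% at L = 28, 32/61 = 52% at L = 60, and 62/91 = 68% at L = 90. The change helps only if scans are mostly done within four weeks.

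**Step 4: the boundary.** Table 6-3 counts a scan on DLD+3 as on-treatment. SAP 8.2.1, read literally, requires it to be before that day. The two differ by one day.

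**The case against.** The 3/28 split follows the division between efficacy and safety consistently. It is a choice, not a contradiction. That stands, and the point is about fit to one measure.

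A reader might infer that early stoppers' scans enter no change analysis at all. The documents do not support that. Endpoint 6 in SAP 8.2.1 plans the change after discontinuation for all available continuous efficacy parameters, SAP 8.2.1.6 spells it out for tumor size, and SAP 8.2.1 exempts it from the on-treatment rule. A late scan is used there whenever an earlier on-treatment scan exists.

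A reader might also infer that most End of Treatment scans are lost. That needs a median lag above 3 days, and no lag is documented.

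Extending the criticism to quality of life and clinical symptoms is tempting too. Quality-of-life scores are covered by endpoint 6, although SAP 8.2.1.7 does not repeat it. Symptoms fall under Table 6-2, and Table 6-1 allows them only 1 week at baseline. Whether either should count as on-treatment four weeks after stopping is debatable.

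The worst-value sensitivity analysis in SAP 8.2.1 addresses missing windows, but it imputes a value where an observed scan exists. Adverse events are collected to 3 months after the last dose in discontinuers, so tumor growth reported as an event would be captured; measured change in volume would not.

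Finally, gap=28 alone does not bring scans before Day 137 into a Month window, and it removes some day-90 pairs. Both objections stand and shape the fix.

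**Conclusion.** The point holds for pituitary imaging. A scan more than 3 days after the last dose leaves the Month windows and the tumor-size mixed model. Without an earlier on-treatment scan it enters no specified change analysis; with one, it is reported as off-drug change over an interval that can be largely on drug (78% and 97% in the two examples, which assume an annual scan at Day 365 and a late scan at DLD+10).

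The number of scans affected cannot be stated. The share outside the gap runs from 0% to 96% over the lags tried, and the documents give no figure for how many patients stop before the first annual scan. Patients scanned while still on treatment are unaffected. This is a worthwhile, inexpensive improvement to a secondary analysis and does not touch the primary safety endpoint.

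**What to change.** Before database lock, edit the SAP as follows.

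1. In Table 6-3 footnote 4 and in SAP 8.2.1, set gap=28 for pituitary imaging, as already applies to gallbladder imaging in that table. Its Day 90 after last dose window then starts at DLD+29.
2. In SAP 8.2.1.6, add a summary of absolute and percentage change in tumor volume from baseline to Last value on treatment. This includes patients who stop before the first post-baseline window opens on Day 137.
3. Use the same boundary, inclusive or not, in SAP 8.2.1 and the window tables.

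Keep gap=3 for UFC, cortisol, ACTH and blood pressure, and do not extend gap=28 to quality of life or clinical symptoms.

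The cost is a footnote, two sentences and one table row, with no new data. Some scans up to 28 days off drug will count as on-treatment. The day-90 tumor change will have fewer pairs: a patient with an annual scan and a single scan at DLD+10 no longer contributes unless there is another scan between DLD+29 and DLD+90.
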